8.2.2 Sample Size

The randomization will be stratified by treatment setting (correction/maintenance) and baseline CRP category (≤ 30 mg/L / >30 mg/L). The stratification will ensure that 20% of patients will be recruited in the correction setting and 80% in the maintenance switch setting.

The expected yearly event rate is approximately 20%, based on

- an expected 25% composite endpoint rate (a mortality rate of approximately 16% [15, 16] and non-fatal cardiovascular morbidity of approximately 9% [17]) in the maintenance setting (80% of patients)
- a 7% rate for the combined endpoint in the correction setting (20% of patients) [CSR BA16738]

Assuming linear recruitment over 30 months and a follow-up time of 18 months after randomization of the last patient, a sample size of 2800 patients, representing approximately 7700 patient-years of exposure, would be adequate to observe 1264 events of the composite endpoint of death and non-fatal cardiovascular events.

1264 events are sufficient to ensure 90% power to establish non-inferiority of MIRCERA® to comparator ESAs in terms of the composite endpoint based on a non-inferiority margin of 1.20 and a one-sided significance level of 0.025.

Duration (months)	NI limit (HR)	Event rate per year	No. events / Nb patients	Expected Event rate at end of study (%)	Highest event rate based on NI limit (%)	Absolute / relative difference (%)	Absolute and relative difference in deaths (%)
48	1.2	0.2	1264 / 2800	45.2	51.2	6.1 / 13	3.6 / 13

Note: The overall event rate observed during the study is considerably lower than that expected at the planning stage. Changing no other parameters leads to an extended study duration; the occurrence of 1264 events has been estimated to be approximately 10 years after study start.

8.2.3 Hypothesis Testing

The primary endpoint is the time between first dose of study medication and the date of death or non-fatal cardiovascular events (MI, stroke), whatever occurs first. The hypotheses to be tested are:

$H_0: h_{MR} \geq 1.20$ versus $H_1: h_{MR} < 1.20$

Using the correspondence between tests and confidence intervals, the test for non-inferiority will be based on the upper limit of the two-sided 95% confidence interval for the hazard ratio of the two groups. When the upper confidence interval limit is lower than 1.20, the MIRCERA® group will be regarded as clinically non-inferior to the reference group. The corresponding p-value will be calculated via the standard normal distribution:

$$p = P(t \leq \hat{T}) = \Phi \left(\frac{\ln \hat{h}_{MR} - \ln 1.20}{SE} \right),$$

where SE denotes the standard error of $\ln \hat{h}_{MR}$ and Φ is the cumulative distribution function of the standard normal distribution.

8.2.4 Analysis Populations

The primary analysis will be performed based on the safety population defined as all patients randomized who receive at least one dose and had at least one post-dose safety assessment.

In addition, the primary analysis will be performed based on the intent-to-treat (ITT) population defined as all patients randomized according to the original treatment assignment.

8.2.5 Efficacy Analysis

This is a safety study; no formal efficacy analyses will be performed. Hemoglobin over time and dose will be analyzed descriptively.

8.2.5.1 Interim Analysis

No formal interim analyses are planned. Safety updates will be prepared for review by the DSMB at its scheduled meetings (see section 10.2).

8.2.6 Other Safety Data Analyses

The safety parameters will be vital signs, AEs and the safety laboratory parameters including iron parameters.

Adverse event data will be presented in frequency tables (overall and by intensity) by body system. In tables showing the overall incidence of adverse events, subjects who experienced the same event on more than one occasion are counted only once in the calculation of the event frequency. Adverse events will be summarized throughout the whole study treatment period and up to 30 days after the last administration of study treatment.

Deaths will be listed and summarized descriptively. Vital signs and laboratory data will be analyzed descriptively and will be assessed for clinically relevant abnormalities as well as changes from baseline. The results of the exploratory statistical analysis of NT-proBNP and troponin T will be reported separately.

Demographic and baseline disease characteristics will be summarized by treatment arm for all randomized patients.

The secondary objectives (incidence of anti-erythropoietin antibody-mediated pure red cell aplasia (PRCA), gastrointestinal bleeding and thromboembolic events), will be analyzed using descriptive statistics and analytical methods such as risk ratios, Cox regression and ANOVA methods.

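### General adverse events get only crude once-per-patient percentages with no person-time, and no main method is named for the secondary safety objectives

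*Combined protocol and SAP*

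**What the plan says.** **General adverse events (section 8.2.6).** The presentation is "Adverse event data will be presented in frequency tables (overall and by intensity) by body system". The counting rule is that "subjects who experienced the same event on more than one occasion are counted only once in the calculation of the event frequency". The window is "Adverse events will be summarized throughout the whole study treatment period and up to 30 days after the last administration of study treatment". No person-time rate, cumulative incidence or summary of time on drug by arm is named. Section 8.2.5 describes dose, but not length of exposure.

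**Secondary objectives (PRCA, gastrointestinal bleeding, thromboembolic events).** The same section says these "will be analyzed using descriptive statistics and analytical methods such as risk ratios, Cox regression and ANOVA methods". The synopsis gives the same list of methods, there also covering hemoglobin over time and dose. Neither place says which method is the main one, over what risk window, or how deaths are handled.

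**Duration.** Section 8.2.2 was built on a 48-month trial: "Assuming linear recruitment over 30 months and a follow-up time of 18 months after randomization of the last patient", "representing approximately 7700 patient-years of exposure". The note added below it says "the occurrence of 1264 events has been estimated to be approximately 10 years after study start". The amendment summary lists no change to section 8.2.6.

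**Design.** The study is open-label (6.4). About 80% of patients are on maintenance therapy (4) and are randomised 1:1 to continue their current ESA or change to MIRCERA (5.2). Withdrawal may follow adverse events, insufficient response, patient choice or administrative reasons, and patients are to be withdrawn at kidney transplantation (4.4).

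**The concern.** A once-per-patient percentage depends on both the event rate and how long patients are observed. When all patients in both arms are followed for the same short time, this does little harm. Here time on drug can run from one dose to about 10 years. In the maintenance setting only one arm changes drug, and everyone knows which arm that is, so earlier stopping in one arm is plausible. The arm with less exposure would then show lower percentages at the same underlying rate.

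This is a post-authorisation safety study, and the adverse event tables are a large part of what it will report. Three named event types are its stated secondary objectives. For those the gap is narrower: a method that uses time at risk is on the list, but so is one that does not, and the choice is left open.

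**Working it through.** **1. The plan's own exposure figure.** With linear recruitment over 2.5 years and 1.5 years of further follow-up, mean potential follow-up is 1.5 + 2.5/2 = 2.75 years. Then 2800 × 2.75 = 7700 patient-years, exactly the stated figure. It covers both arms together and allows for no stopping of any kind. It therefore says nothing about exposure by arm.

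**2. Potential follow-up now.** If recruitment took the planned 30 months and the trial ends 10 years after its start, the mean is 10 − 2.5/2 = 8.75 years.

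**3. Simple illustration (assumed rates and exposures).** Treat every patient in an arm as exposed for E years at a constant event rate λ per year. Crude incidence is 1 − exp(−λE).
- Equal rates, λ = 0.03, 4 versus 5 years: 1 − exp(−0.12) = 11.3%; 1 − exp(−0.15) = 13.9%; risk ratio 0.81.
- Equal rates, 3 versus 4 years: 8.6% versus 11.3%; risk ratio 0.76.
- True 25% excess in the arm exposed for 4 years (λ = 0.0375, against 0.03 over 5 years): both exponents are 0.15, so 13.9% versus 13.9%; risk ratio 1.00.
- Equal rates and equal exposure: risk ratio 1.00.

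**4. A model with stopping (all hazards assumed).** Let h be the event hazard, d the stopping hazard, T the potential follow-up, and w = 30/365.25 years. Crude incidence is C = ∫₀ᵀ h·exp(−ht)·R(t) dt, where R(t) = 1 up to w and exp(−d(t − w)) after that. Mean time on drug is (1 − exp(−dT))/d. The reference arm has d = 0.15 per year and h = 0.03 per year throughout.

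| d, other arm | Mean years on drug (other vs reference), T = 8.75 | Crude incidence, equal h, T = 8.75 | Crude risk ratio, equal h, T = 8.75 | Crude risk ratio, equal h, T = 4 | Crude risk ratio, true hazard ratio 1.25, T = 8.75 |
|---|---|---|---|---|---|
| 0.15 | 4.87 vs 4.87 | 13.4% vs 13.4% | 1.00 | 1.00 | 1.22 |
| 0.20 | 4.13 vs 4.87 | 11.5% vs 13.4% | 0.86 | 0.92 | 1.05 |
| 0.25 | 3.55 vs 4.87 | 10.0% vs 13.4% | 0.75 | 0.85 | 0.91 |
| 0.30 | 3.09 vs 4.87 | 8.8% vs 13.4% | 0.66 | 0.79 | 0.81 |

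With h from 0.01 to 0.10 per year and d = 0.20 to 0.30 in the other arm, the crude risk ratio at T = 8.75 runs from 0.65 to 0.87 with no true difference. If the reference arm stopped earlier instead, the ratio would move above 1.

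**5. What person-time does.** Person-time to first event in the same window is ∫₀ᵀ exp(−ht)·R(t) dt = C/h. Events divided by person-time is therefore C/(C/h) = h in each arm. With equal hazards the rate ratio is 1.00 whatever the two values of d. This needs a constant hazard and stopping unrelated to risk.

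**The case against.** **Unequal exposure is assumed.** This is the strongest point on the other side, and it stands. The documents give no discontinuation figure by arm. Allocation is 1:1, the end of study applies to everyone still in it (3.1.3), and the withdrawal rules are the same for both arms (4.4). Long follow-up alone does not bias the comparison: the first row of the table shows 1.00. A reader might infer that the adverse event results will be biased. The documents support only that they could be, and that the planned tables would not reveal it.

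**The secondary objectives are not limited to crude methods.** A reader might infer from the risk ratio that they are. Section 8.2.6 and the synopsis both name Cox regression, which uses time at risk. What remains is that the main method is not chosen.

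**The 30-day window is stated for adverse events.** A reader might extend it to the secondary objectives, but no analysis window is stated for them. For PRCA, section 7.4 continues study assessments after a confirmed case, with antibody testing until the end of the study. Section 7.2.1 collects related serious events whatever the time since the last dose. In practice, bleeding and thromboembolic events arrive through adverse event reporting (5.4.1, 7.2.1), so the collection period limits them too. That is a reason to state the window.

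**ANOVA may not be meant for incidence data.** In the synopsis the method list also covers hemoglobin and dose, where ANOVA fits. Section 8.2.6 shortens that sentence, so nothing is claimed here on that point.

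**The adverse event tables are descriptive.** They carry no test, and death, MI and stroke are analysed by Kaplan-Meier and Cox methods (8.2.1). This keeps the point modest. It does not remove it, because readers will compare the two columns.

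**Conclusion.** The point holds as a low-cost improvement. For general adverse events, section 8.2.6 specifies a crude proportion with no person-time denominator and no display of exposure by arm. In an open-label stay-or-switch trial expected to last about 10 years, that could turn equal rates into a crude risk ratio of about 0.65 to 0.87, or shrink a true hazard ratio of 1.25 to 1.05 or push it below 1. Those sizes rest on assumed stopping hazards of 0.20 to 0.30 versus 0.15 per year, constant hazards, and 8.75 years of potential follow-up. With equal stopping there is no spurious difference.

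For the secondary objectives the conclusion is narrower: a crude risk ratio remains an allowed analysis beside Cox regression, with neither named as the main one. The primary analysis is not touched.

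**What to change.** In section 8.2.6:

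1. **General adverse events.** Add a summary of time on drug by arm. Beside the frequency tables, give events per 100 patient-years on treatment plus 30 days, with rate ratio and 95% CI.
2. **Gastrointestinal bleeding and thromboembolic events.** Make the Cox model already listed the main analysis in place of the crude risk ratio: cause-specific, with deaths censored. Add cumulative incidence curves that treat death as a competing event. State the risk window, and match it to the periods in which events are collected (5.4.1, 7.2.1).
3. **PRCA.** Report counts with exact Poisson limits per patient-year. The educational program in Appendix 5 calls this side effect very rare, so a model would add little.

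The cost is a few extra tables. Drug administration and adverse events are already recorded at monthly visits (Table 1), so no new data are needed. One limit should be stated in the plan: person-time rates, and a Cox model censored at the end of the window, correct for length of exposure but not for stopping that is related to the patient's risk.

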9. DATA COLLECTION, MANAGEMENT AND QUALITY ASSURANCE

The overall procedures for quality assurance of clinical study data are described in the Roche Standard Operational Procedures.

Data for this study will be recorded via an Electronic Data Capture (EDC) system using electronic Case Report Forms. It will be transcribed by the site from the paper source documents onto the eCRF. (In no case is the eCRF to be considered as source data for this trial.)

Accurate and reliable data collection will be assured by verification and cross-check of the eCRFs against the investigator's records by the study monitor [source document verification], and the maintenance of a drug-dispensing log by the investigator.

A comprehensive validation check program utilizing front-end checks in the eCRF and back-end checks in the Roche database will verify the data and discrepancies will be generated accordingly. These are transferred electronically to the eCRF at the site for resolution by the investigator.

Throughout the study the SMT will review data according to the SMT Data Review Plan as described in the Data Quality Plan.

9.1 Assignment of Preferred Terms and Original Terminology

For classification purposes, preferred terms will be assigned by the Sponsor to the original terms entered on the eCRF, using the most up-to-date version of the Medical Dictionary for Regulatory Activities (MedDRA) terminology for adverse events and diseases and the International Non-proprietary Name (INN) Drug Terms and Procedures Dictionary for treatments and surgical and medical procedures.

10. STUDY COMMITTEES

10.1 Steering Committee

A Steering Committee will be put in place consisting of a group of study investigators and representatives of the Sponsor. The tasks of the Steering Committee include protocol development, review of study conduct, and management of issues arising during the trial.

10.2 DSMB

An independent Data and Safety Monitoring Board (DSMB) consisting of 3 clinical experts in the field and a statistician will be constituted to review the safety data, including adjudicated outcomes, collected during the study. A non-voting clinical scientist representative of Roche will also be available to assist the DSMB with clarification of issues related to the protocol and study management.

The board will review baseline risk factors as specified in section 5.3 and the safety data when approximately 25% (316) of the required events have been recorded and adjudicated. In addition, the board will review the data when 50% (632) and 75% (948) of events have occurred. Following each meeting the DSMB will give recommendations regarding continuation or discontinuation of the study to the sponsor according to pre-specified rules recorded in the DSMB charter.

The Board may recommend stopping the study due to safety reasons, as described in the DSMB charter.

The analyses provided to the DSMB will be prepared by an external independent statistician from the independent data coordinating center (iDCC). Further details about the role and procedures of the DSMB will be provided in the DSMB charter.

10.3 Endpoint Committee

An independent Endpoint Adjudication Committee will be constituted to review all potential endpoint events. The Endpoint Adjudication Committee will consist of at least two cardiologists, one nephrologist and one neurologist with experience in clinical studies and in the adjudication of study endpoints. The committee will provide a blinded assessment of fatal and non-fatal events in the composite endpoint.

Suspect events will be recorded by the treating personnel in the dialysis centers. The Sponsor will supply the Committee members with blinded patient level data for review. For the list of documents see [Appendix 6](#). The suspect events will be adjudicated by blinded committee members, with subsequent blinded adjudication in the case of disagreement.

The Endpoint Committee and the Sponsor will establish the classification definitions in accordance with the study protocol before the adjudication process begins. Further details about the role and procedures of the Endpoint Committee will be provided in a separate document, the Endpoint Adjudication Committee charter.

12. ETHICAL ASPECTS

12.1 Local Regulations/Declaration of Helsinki

The investigator will ensure that this study is conducted in full conformance with the principles of the “Declaration of Helsinki” or with the laws and regulations of the country in which the research is conducted, whichever affords the greater protection to the individual. The study must fully adhere to the principles outlined in “Guideline for Good Clinical Practice” ICH Tripartite Guideline or with local law if it affords greater protection to the subject. For studies conducted in the EU/EEA countries, the investigator will ensure compliance with the EU Clinical Trial Directive [2001/20/EC]. For studies conducted in the USA or under US IND, the investigator will additionally ensure adherence to the basic principles of “Good Clinical Practice” as outlined in the current version of 21 CFR, subchapter D, part 312, “Responsibilities of Sponsors and Investigators”, part 50, “Protection of Human Subjects”, and part 56, “Institutional Review Boards”.

In other countries where a “Guideline for Good Clinical Practice” exists, Roche and the investigators will strictly ensure adherence to the stated provisions.

12.2 Informed Consent

Written Informed Consent from Subjects:

It is the responsibility of the investigator, or a person designated by the investigator [if acceptable by local regulations], to obtain signed informed consent from each subject prior to participating in this study after adequate explanation of the aims, methods, anticipated benefits, and potential hazards of the study. For the subject not qualified or incapable of giving legal consent, written consent must be obtained from the legally acceptable representative. In the case where both the subject and his/her legally acceptable representative are unable to read, an impartial witness should be present during the entire informed consent discussion. After the subject and representative have orally consented to participation in the trial, the witness’ signature on the form will attest that the information in the consent form was accurately explained and understood. The investigator or designee must also explain that the subjects are completely free to refuse to enter the study or to withdraw from it at any time, for any reason. The electronic Case Report Forms (eCRFs) for this study contain a section for documenting subject informed consent, and this must be completed appropriately. If new safety information results in significant changes in the risk/benefit assessment, the consent form should be reviewed and updated if necessary. All subjects (including those already being treated) should be informed of the new information, given a copy of the revised form and give their consent to continue in the study.

For non-US-IND studies:In a life-threatening situation where a patient is unconscious or otherwise unable to communicate, the emergency is such that there is not enough time to obtain consent from the patient's legally acceptable representative, and there is no other or better treatment available, it is permissible to treat the patient under protocol with consent of the investigator, with appropriate documentation that the IEC had approved

the procedures used to enroll patients in such situations. In addition, the patient or his/her legally acceptable representative should be informed about the trial as soon as possible and consent to continue, giving written consent as described above.

12.3 Independent Ethics Committees/Institutional Review Board

Independent Ethics Committees (IECs) [non-US] For EEA member states, the sponsor will submit to the Competent Authority and Ethics Committees the protocol and any accompanying material provided to the subject (such as subject information sheets or descriptions of the study used to obtain informed consent as well as any advertising or compensation given to the subject).

Approval from the committee must be obtained before starting the study, and should be documented in a letter to the investigator specifying the date on which the committee met and granted the approval.

Any modifications made to the protocol after receipt of the IEC's approval must be re-submitted by the investigator in the US and by the Sponsor in the EEA member states in accordance with local procedures and regulatory requirements.

When no local review board exists, the investigator is expected to submit the protocol to a regional committee. If no regional committee exists, Roche will assist the investigator in submitting the protocol to the European Ethics Review Committee.

Institutional Review Board [US]: It is the understanding of the sponsor that this protocol [and any modifications] as well as appropriate consent procedures and advertisements, will be reviewed and approved by an Institutional Review Board. This board must operate in accordance with the current Federal Regulations. The sponsor will receive a letter or certificate of approval prior to initiation of the study, and also whenever subsequent amendments/modifications are made to the protocol.

13. CONDITIONS FOR MODIFYING THE PROTOCOL

Requests from investigators to modify the protocol to ongoing studies will be considered only by consultation between an appropriate representative of the sponsor and the investigator [investigator representative[s] in the case of a multicenter trial]. Protocol modifications must be prepared by a representative of the sponsor and initially reviewed and approved by the Clinical Science Leader/Clinical Pharmacologist and Biostatistician.

All protocol modifications must be submitted to the appropriate Independent Ethics Committee or Institutional Review Board for information and approval in accordance with local requirements, and to Regulatory Agencies if required. Approval must be obtained before any changes can be implemented, except for changes necessary to eliminate an immediate hazard to trial subjects, or when the change[s] involves only logistical or administrative aspects of the trial [e.g. change in monitor[s], change of telephone number[s]].

